## 3.0 Subject ELIGIBILITY

### 3.1 Inclusion Criteria

18 years and older male or female patients

Ipsilateral intact biopsy-proven invasive breast cancer clinical T1-T4 (by imaging)

- 3.1.1 Available mammography and ultrasound imaging of the existing index cancer, with orthogonal measurements
- 3.1.2 Prior history of ipsilateral or contralateral breast cancer, presenting with a new primary or recurrent disease
- 3.1.3 Patients who were determined to be candidates for either neoadjuvant chemotherapy or neoadjuvant endocrine therapy by the treating physician

### 3.2 Exclusion Criteria

- 3.2.1 History of ipsilateral mastectomy.
- 3.2.2 Women who already started neoadjuvant chemotherapy or endocrine therapy.
- 3.2.3 Woman who may be pregnant.
- 3.2.4 Prior history of anaphylactic or anaphylactoid reaction to any contrast.
- 3.2.5 Prior allergy to iodine or iodinated contrast.

Imaging Services will practice safe contrast administration through the evaluation of the patients' history via the electronic medical record and/or patient questionnaire.

Individualized, patient centric protocol planning, medication review, and contrast dosage will be utilized to reduce adverse events. Renal function testing is not routinely required for every patient receiving contrast. Creatinine and Estimated Glomerular Filtration Rate (eGFR) testing will be performed on patients at risk for contrast induced nephrotoxicity (CIN). Patients with reduced eGFR may be given intravenous (IV) iodinated contrast safely in many circumstances. Clinically significant nephrotoxicity after iodinated contrast media administration is highly unusual in patients with normal or mildly reduced renal function **GFR is tested in patients with a risk factor for decreased renal function.** Patients with one or more of the following conditions are considered to be at high risk for contrast induced nephropathy (CIN). These patients will be required to have renal function testing (eGFR) within 30 days before receiving intravenous iodinated contrast.

#### i) Kidney problems

- ii) Kidney surgery
- iii) Gout
- iv) Hypertension
- v) Diabetes mellitus
- vi) Age > 60

Patients with known distant metastasis.

#### 4.0 CEDM RESPONSE ASSESSMENT PLAN

Patients diagnosed with invasive breast cancer with available mammography and ultrasound imaging are eligible for the study.

##### 3.2.6

Eligible patients will be imaged at baseline (before initiation of neoadjuvant chemotherapy or endocrine therapy), early (2-4 cycles of neoadjuvant therapy) and late (after completion of neoadjuvant chemotherapy or endocrine therapy) timepoints with mammography. CEDM will be done within 2 weeks of the specified timepoint. Three dimensional orthogonal measurements will be obtained in all timepoints. Additional sites of disease in the ipsilateral or contralateral breast identified by CEDM will be recorded and reported. ACR BI-RADS MRI lexicon will be used for reporting.

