**5.1.2** **Medical history, and reviewing subject eligibility criteria previous and concomitant medications**

#### **Informed Consent**

#### **5.2 Procedures During CEDM**

CEDM will be performed using UTSW Imaging Protocol (**attached, Appendix A**), including monitoring for immediate contrast reactions.

Discussion of additional findings: All breast imaging findings are routinely discussed with the patient by the radiologist immediately after imaging in our clinical practice. Additional findings identified on CEDM will be addressed similar to additional disease noted on ultrasound or breast MRI per standard of care.

Study Number – Insert PRMC Assigned SCCC- Protocol Number (found on the PRMC approval letter)

---

Survey of patient experience with CEDM and other pre-operative imaging such as MRI will be collected after CEDM is performed, optimally at pre-operative time point (Appendix B).

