## **6.3 Pathology**

Final histopathology for correlation will include the size of residual tumor (ypT), tumor cellularity (%) and amount of DCIS (%). Per AJCC8th edition [Amin MB, Edge SB, Greene FL, et al, eds. AJCC Cancer Staging Manual. 8th ed. New York: Springer; 2017] (ypT) is based on the largest continuous focus of residual invasive cancer, if present. Treatment-related fibrosis adjacent to residual invasive carcinoma or between foci of residual cancer is not included in the ypT maximum dimension. When multiple foci of residual tumor are present, the (m) modifier is included.

In addition, we will record ki67 index pre and post therapy and its potential correlation with the degree of tumor response seen on CEDM.

The agreement between pre-operative CEDM measurements and mammography in categorizing tumor response RCB0-I/ RCBII/RCBIII will be assessed using weighed kappa.

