### **8.3 Data Analyses**

Descriptive statistics will be produced for all patients; frequencies and percentages for categorical measures and means, medians, standard deviations, and ranges for continuous measures. The number of cancer foci identified by each imaging modality will be compared. Tumors will be categorized according to immunohistochemical approximated molecular profiles (Luminal A, Luminal B, Triple-negative and HER-2 amplified). Additional exploratory analyses will be performed as needed.

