#### **1. Sensitivity of CEDM versus mammography**

Histopathological assessment will be used as the reference standard.

For categorical measurements of tumor response (CR/PR/SD/PD or RCB0-I /RCB II /RCB III):

1. Sensitivities and specificities in predicting pCR (or RCB0) will be calculated for CEDM and mammography respectively.
2. The agreement between CEDM and mammography in categorizing tumor response (CR/PR/SD/PD or RCB0-I/ RCBII/RCBIII) will be assessed using weighed kappa.

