#### **2. For continuous measurements of tumor response (RECIST, percent change in tumor volume and pre-surgery lesion size):**

1. ROC analysis will be used to assess the diagnostic performance of CEDM and mammography. The Area under the ROC curve (AUC) will be compared. A leave-one-out cross validation algorithm will be used to reduce bias from overfitting.
2. The agreement between CEDM and mammography in RECIST, percent change in volume and pre-surgery lesion size will be assessed using intraclass correlation (ICC).

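### The plan does not say when the early and late mammography values are recorded relative to that timepoint's CEDM subtraction images, so the comparison in 8.3 may not rest on separately made readings

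*Combined protocol and SAP*

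**What the plan says.** **Acquisition.** Section 4.0 (text printed under 3.2.6) has patients imaged with mammography at baseline, early and late timepoints. It adds "CEDM will be done within 2 weeks of the specified timepoint", and then "Three dimensional orthogonal measurements will be obtained in all timepoints". It does not say who measures, which modality is read first, or when a mammography value becomes final.

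**Interpretation.** Section 4.1 sends the CEDM images to the radiologist. It describes the low-energy images as identical to ordinary unenhanced mammograms and has them used in the same interpretation. Section 5.2 says "All breast imaging findings are routinely discussed with the patient by the radiologist immediately after imaging in our clinical practice". The time and events table in 5.4 lists CEDM at all three visits and no separate mammogram.

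**Analysis.** Section 8.3 states "The number of cancer foci identified by each imaging modality will be compared". Under item 1, "Sensitivities and specificities in predicting pCR (or RCB0) will be calculated for CEDM and mammography respectively"; under item 2, for the continuous measures, "The Area under the ROC curve (AUC) will be compared". Agreement between the modalities is to be assessed by weighted kappa (6.3 and 8.3, item 1) and by ICC (8.3, item 2). The Study Summary words the primary objective as a comparison with mammography. Objective 2.1.1 and the primary endpoint in 2.4.1 and 8.1 name no comparator.

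**The concern.** Every mammography input to these comparisons is a value that a reader produces. A reader who has already seen where a lesion enhances, and how far, may measure or count differently on the unenhanced image. The two sets of values would then not be made separately, and nothing in 8.3 can separate them afterwards.

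The direction is not known. Borrowing from CEDM pulls mammography towards it and shrinks a true AUC difference. A reader who shares the hypothesis in 1.3 that CEDM is superior could score mammography lower and widen the difference. Kappa and ICC would tend to rise with borrowing.

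At stake are the AUC difference, the paired sensitivities and specificities, the foci counts and the agreement statistics. Section 8.2 says the results will help design a larger multi-institutional comparison, so a distorted difference could carry over into that design.

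**Working it through.** **1. Is there a rule anywhere?** Sections 4.0, 4.1, 5.2, 5.4, 6.0 to 6.3, 8.3 and 9.4 contain no reading order, masking, washout or lock. The unblinded label in the Summary and the not-applicable entry in 7.3 describe the design and say nothing about how images are read. The supplied Appendix A covers indications, pregnancy, kidney function and metformin, and stops there.

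**2. Which readings are exposed?**
- Baseline: largely protected, because 3.1.1 requires mammography with measurements at entry.
- Early and late, separate mammogram read at once and before CEDM: protected from that timepoint's CEDM. The 2-week window in 4.0 does not guarantee this order.
- Early and late, low-energy image as comparator: exposed unless an order is set, because it arrives with the subtraction images and is interpreted with them.

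**3. The plan's own precision figures (8.2).** With 100 patients and 40% pCR there are 40 pCR and 60 non-pCR patients.
- Sensitivity: 1.96 × √(0.25/40) + 1/80 = 0.1549 + 0.0125 = 0.167 (stated 0.17).
- Specificity: 1.96 × √(0.25/60) + 1/120 = 0.1265 + 0.0083 = 0.135 (stated 0.14, rounded up).
- AUC, largest half-width: 0.116 by Hanley-McNeil, 0.113 by the binormal variance (stated 0.12, rounded up).
- Spearman width at zero correlation: 2 × tanh(1.96/√97) = 0.393 (stated 0.39).

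All four reproduce. They concern one modality at a time and do not depend on reading order.

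**4. Illustration of size.** The documents give no CEDM AUC, no correlation between modalities and no carry-over rate. All three are assumed here.
- Mammography AUC: 1.2 gives sensitivity 54.2% and specificity 86.3% for pCR. With an equal-variance binormal model, separation = 0.105 + 1.094 = 1.199 and AUC = Φ(1.199/√2) = 0.802.
- Assumed CEDM AUC: 0.90, 0.85, or equal to mammography. Assumed within-class correlation: 0.3 to 0.7.

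*(a) Mammography value copied from CEDM in a share q of patients.* The observed AUC is (1 − q) × 0.802 + q × AUC of CEDM, so the observed difference is (1 − q) × the true difference.

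| True difference | q = 10% | q = 20% | q = 30% |
|---|---|---|---|
| 0.098 (CEDM 0.90) | 0.088 | 0.079 | 0.069 |
| 0.048 (CEDM 0.85) | – | 0.039 | – |
| 0 | 0 | 0 | 0 |

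*(b) Opposite bias: mammography separation read 10% lower.* AUC = Φ(0.9 × 1.199/√2) = 0.777, so the difference grows by 0.024.

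*Sampling error.* The simulated paired 95% half-width for the AUC difference (40 versus 60 patients, 6,000 replicates) is about 0.07 to 0.10 at CEDM AUC 0.85 to 0.90, and up to 0.11 at equal AUCs.

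*Coverage.* A nominal 95% interval would cover the true difference 90% to 95% of the time under (a) with q = 20%, and 90% to 93% under (b).

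*Agreement.* Under (a) with q = 20%, the pooled ICC, 2 × covariance/(sum of the two variances), moves from 0.48–0.78 to 0.58–0.83.

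**The case against.** The best case for leaving the plan alone is that the mammography contrast is not the primary quantity. Objective 2.1.1 and the primary endpoint in 2.4.1 and 8.1 name no comparator, and secondary objective 2.2.1 names none. Section 8.2 calls the study exploratory and leaves comparison with other modalities to a later, larger study. No document figure supports any carry-over rate, and every shift shown above is below sampling error. The likelier direction, shrinkage, works against the study's own hypothesis. If mammography is a separate examination done first and read at once, the order is already right in practice.

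Most of this stands, and it limits the weight. It does not remove the point, because the Summary and 8.3 still plan the comparison and the order cannot be restored once values are recorded.

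A reader might infer more than the documents support:
- *That the unblinded label shows mammography will be read with CEDM in view.* It is a design label, and 7.3 concerns unblinding procedures. Neither sets a reader rule.
- *That the primary CEDM AUC or the precision figures in 8.2 are compromised.* They concern CEDM alone and are unaffected.
- *That using low-energy images in the CEDM interpretation is a fault.* It is part of the test. The gap concerns how the mammography value is obtained.
- *That 5.4 shows no mammogram is done.* The table may list study procedures only.

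**Conclusion.** The point holds as a cheap improvement of minor to moderate weight. The supplied text does not ensure that early and late mammography values are fixed before that timepoint's subtraction images are seen, and it leaves open what the mammography comparator is. If the comparator is the low-energy image, or a mammogram read after CEDM, the AUC difference and the other paired results in 8.3 may be biased, with unknown direction and size.

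Under the assumed carry-over, the AUC difference moves by about 0.01 to 0.03, against a sampling half-width of about 0.07 to 0.11. The shift is systematic, so an interval for the difference would not reflect it. These figures are illustrative and do not measure harm. Confidence is medium, because a rule in an unsupplied part of Appendix A cannot be excluded.

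**What to change.** In 4.0 and 6.1:

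1. State whether the mammography comparator is a separate mammogram or the CEDM low-energy images, and reconcile 4.0, 4.1 and the table in 5.4.
2. At the early and late timepoints, enter mammography measurements, response category and number of foci in REDCap and lock them before that timepoint's subtraction images are opened. Use only locked values as the mammography arm in 8.3; at baseline, use the measurements already required at entry. Flag any mammogram read after CEDM, and report the AUC difference with and without flagged cases.
3. Report that CEDM was read with knowledge of the mammogram. Report also that memory of, or access to, earlier-timepoint CEDM may still affect both the AUC difference and the kappa and ICC agreement.

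**Cost.** A few sentences and one locked form in the capture system already named in 9.4, with no extra examination or reader. 100 patients × 2 timepoints = 200 short entries; at an assumed 1 to 2 minutes each, 200 to 400 minutes, or about 3 to 7 hours in total.

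**Downsides.** The reading order becomes fixed. Where mammography is acquired with or after CEDM, the subtraction reading waits for the mammography entry, which must fit the same-visit discussion in 5.2. Mammograms done on a later day than CEDM stay unprotected and can only be flagged. With one reader, CEDM can still be drawn towards the locked mammogram, so agreement may remain inflated. No stated sample size or precision figure changes.

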##### 4.1 CEDM

To perform a CEDM examination, an IV is placed in the forearm or antecubital vein and a low osmolar iodinated contrast agent is administered at approximately 3ml/s using a power injector. Contrast agents with iodine concentration between 300 mg/ml and 370 mg/ml are typically used. The volume of contrast is similar to that used for a CT scan, approximately 1.5 ml/kg body weight, typically around 90-150 ml. After a delay of at least 90 seconds from the end of the injection, the patient is positioned for 2 standard mammography views (craniocaudal and mediolateral oblique) of each breast. Rather than a standard single energy mammogram, however, the CEDM device acquires dual-energy image pairs in each projection. Since there is less than 1 second between the low-energy and high energy images, the imaging time is the same as that needed for a standard mammogram. Additional projections may be obtained since optimally enhanced images can typically be obtained up to 7-10 minutes following injection. Following image acquisition, contrast-enhanced subtraction images are produced using a weighted logarithmic subtraction of the low energy image from the high energy image. Because the difference in iodine absorption between the images is larger than the difference in tissue absorption, this dual energy subtraction technique has the effect of increasing the visibility of the iodine while almost completely eliminating the visibility of background tissue. The resulting images will be sent to a review workstation or PACS for interpretation by the radiologist. The low energy images, which are identical to standard unenhanced mammograms, will also be used in the interpretation.

##### 4.1.1

The risks of CEDM include the risks of contrast administration including allergic reactions and renal function abnormalities. Just as with CT, patients will be screened for allergy history and possible renal function abnormalities. Allergic or physiologic reaction are reported to occur in less than 1% of patients when using low osmolar contrast agents although this increases in patients with prior reactions (11,12). Severe acute reactions occur in 4/10,000 (0.04%) of patients (13). Any contrast reaction will be handled in accordance with the Radiology Department's Contrast-Reaction Guidelines  
[https://hs.swmed.edu/communities\\_collaboration/radpoint/clinicaloperations/Practice%20Guidelines%20%20Procedures/Contrast%20Reactions%20-](https://hs.swmed.edu/communities_collaboration/radpoint/clinicaloperations/Practice%20Guidelines%20%20Procedures/Contrast%20Reactions%20-)

%20Pocket%20Guide.pdf#search=contrast%20reaction)Concomitant Medications/Treatments

#### **4.2 Other Modalities or Procedures**

Every effort will be made to perform any additional imaging such as ultrasound and contrast-enhanced breast MRI at the same timepoint with CEDM, however patients will not be excluded based on inability to perform these imaging.

#### **4.3 Duration of Follow Up**

Adverse reactions to contrast will be monitored according to institutional guidelines. Patients will be observed for at least 30 minutes after contrast administration for any immediate side effects of contrast. Only contrast-specific side effects will be recorded, including moderate to severe allergic reactions to contrast, laryngospasm, angioedema, hypotension, bradycardia, diffuse hives.

Overall study duration is expected to be approximately 4-6 months from initiation of neoadjuvant therapy until final surgery in which negative margins are achieved.

#### **4.4 Removal of Subjects from Protocol Therapy**

Subjects will be removed from therapy when any of the criteria listed in Section 5.5 apply. Notify the Principal Investigator and document the reason for treatment discontinuation and the date of discontinuation. The subject should be followed-up per protocol.

#### **4.5 Subject Replacement**

Loss of any subjects before second timepoint CEDM occurs will result in subject replacement.

### **5.0 STUDY PROCEDURES**

#### **5.1 Screening/Baseline Procedures**

Assessments performed exclusively to determine eligibility for this study will be done only after obtaining informed consent. Assessments performed for clinical indications (not exclusively to determine study eligibility) may be used for baseline values even if the studies were done before informed consent was obtained.

**5.1.1** All screening procedures must be performed within 30 days prior to registration unless otherwise stated. The screening procedures include:

**5.1.2** **Medical history, and reviewing subject eligibility criteria previous and concomitant medications**

#### **Informed Consent**

#### **5.2 Procedures During CEDM**

CEDM will be performed using UTSW Imaging Protocol (**attached, Appendix A**), including monitoring for immediate contrast reactions.

Discussion of additional findings: All breast imaging findings are routinely discussed with the patient by the radiologist immediately after imaging in our clinical practice. Additional findings identified on CEDM will be addressed similar to additional disease noted on ultrasound or breast MRI per standard of care.

Study Number – Insert PRMC Assigned SCCC- Protocol Number (found on the PRMC approval letter)

---

Survey of patient experience with CEDM and other pre-operative imaging such as MRI will be collected after CEDM is performed, optimally at pre-operative time point (Appendix B).

**5.3 Follow-up Procedures**

Patients' medical records will be followed 30 days after completion of definitive surgery to collect final pathology outcomes, or if they develop progressive disease.

**5.4 Time and Events Table**

	Baseline	Mid chemotherapy	Pre-Operative
Informed Consent	x		
History and allergies	X	X	X
CEDM	X	X	X
QUESTIONNAIRE			X

**5.5 Removal of Subjects from Study**

Subjects can be taken off the study at any time at their own request, or they may be withdrawn at the discretion of the investigator for safety, behavioral or administrative reasons. The reason(s) for discontinuation will be documented and may include:

- 5.5.1 Subject voluntarily withdraws from treatment (follow-up permitted);
- 5.5.2 Subject withdraws consent (termination of treatment and follow-up);
- 5.5.6 Treating physician judges continuation on the study would not be in the subject's best interest;
- 5.5.7 Subject becomes pregnant (pregnancy to be reported along same timelines as a serious adverse event);
- 5.5.9 Patient develops moderate to severe reaction to contrast (as defined by the Department's guidelines for iodinated contrast) over the course of neoadjuvant therapy follow-up. Mild reactions will be considered for pre-medication and decided on a case by case basis.

**6.0 Measurement of Effect**

Response assessments will be performed in early and late (post chemotherapy and pre-surgery) timepoints. Every effort will be made to obtain CEDM during within 2 weeks of .

**6.1.1**

Response to therapy will be assessed for each patient as follows:

**6.1 Response Evaluation Criteria**

Response evaluation criteria in solid tumors (RECIST) 1.1 criteria, considering the sum of the largest dimension of malignancies at baseline and its variation at subsequent measurements . Clinical response is classified as follows: complete response (CR, disappearance of all lesions); partial response (PR,  $\geq 30\%$  dimensional reduction), stable disease (SD,  $< 30\%$  dimensional reduction/ $< 20\%$

Study Number – Insert PRMC Assigned SCCC- Protocol Number (found on the PRMC approval letter)

---

dimensional increase) and progressive disease (PD,  $\geq 20\%$  dimensional increase).

**For pathologic response, RCB index is assessed routinely per standard of care, where a complete pathologic response has an RCB of zero, and residual disease is classified into three categories (RCB-I, RCB-II, and RCB-III)**

[http://www3.mdanderson.org/app/medcalc/index.cfm?pagename=jsconvert\\_3](http://www3.mdanderson.org/app/medcalc/index.cfm?pagename=jsconvert_3)

---

**6.1.2** This is not a treatment study. Patients will be treated either as per standard of care neoadjuvant protocol or as part of ongoing treatment trials in the UT Southwestern Medical Center.

Percent change in tumor volume using the following formula for ellipsoidal/spherical volume derived from mid-dynamic sequence subtraction series:  $V (\text{cm}^3) = (4/3 \pi) \times \text{length}/2 \times \text{width}/2 \times \text{height}/2$

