**Table 1. Standard imaging methods used to monitor response to neoadjuvant therapy**

Table 1			
Current Breast Imaging Utilized Prior to Neoadjuvant Therapy			
Variable	Mammography*	Breast US†	Breast MR Imaging‡
Ipsilateral breast	Extent of disease evaluation: full-field craniocaudal, full-field mediolateral oblique, full-field mediolateral/ lateromedial plus spot compression craniocaudal, spot compression mediolateral/ lateromedial	Extent of disease evaluation targeted to index lesion	Extent of disease evaluation: pectoralis/ chest wall invasion
Contralateral breast	Screening: full-field craniocaudal, full-field mediolateral oblique	Not typically performed	Screening
Lymph nodes§	Lymphadenopathy evaluation: axillary (incomplete)	Lymphadenopathy evaluation: axillary	Lymphadenopathy evaluation: axillary, internal mammary

\* Digital breast tomosynthesis may be utilized as part of the diagnostic evaluation. Substitute spot compression views with magnification craniocaudal and mediolateral/lateromedial views if associated microcalcifications.

† Whole-breast US may be performed for patients unable to undergo magnetic resonance (MR) imaging, particular for patients with mammographically dense breasts. However, the relatively high rate of false-positive findings limits recommendation of this approach.

‡ Utilization of breast MR imaging may vary with clinical practices due to surgeon and/or oncologist preferences.

§ Fluorine 18 fluorodeoxyglucose (FDG) positron emission tomography (PET)/computed tomography (CT) imaging may be helpful for evaluating regional nodal sites of disease (axilla, internal mammary, and supraclavicular) for locally advanced breast cancer, especially in patients presenting with more advanced axillary disease.

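### RCB 0 is the only pCR reference, so node-positive patients whose breast is clear but whose nodes are not lower the specificity of breast-only imaging, more so for the more accurate modality

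*Combined protocol and SAP*

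**What the plan says.** Section 3.1 admits "Ipsilateral intact biopsy-proven invasive breast cancer clinical T1-T4 (by imaging") and sets no N category. The only stage-based exclusion in section 3.2 is "Patients with known distant metastasis". Node-positive patients are therefore eligible.

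For CEDM (section 4.1) the patient is "positioned for 2 standard mammography views (craniocaudal and mediolateral oblique) of each breast". Section 4.0 asks for three orthogonal measurements and for extra disease sites in either breast. Section 6.1.3 records lesion dimensions, enhancement, residual calcification and the clip. Imaging complete response in section 6.1 is "complete response (CR, disappearance of all lesions"), with no rule for reading nodes. The ROC inputs in section 8.3 are RECIST, change in tumour volume and pre-surgery lesion size. For lymph nodes, Table 1 lists under mammography "Lymphadenopathy evaluation: axillary (incomplete").

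On the reference side, section 6.1 uses the RCB index, "where a complete pathologic response has an RCB of zero, and residual disease is classified into three categories (RCB-I, RCB-II, and RCB-III"). Section 8.3 then states: "Sensitivities and specificities in predicting pCR (or RCB0) will be calculated for CEDM and mammography respectively". Section 6.3 lists the pathology items: "Final histopathology for correlation will include the size of residual tumor (ypT), tumor cellularity (%) and amount of DCIS". It has no nodal item. No breast-only pCR, nodal stratum or sensitivity analysis is specified. Appendix C classifies ypT and ypN separately and says that ypT0 with only lymphovascular invasion (LVI) cannot be called pCR.

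**The concern.** The index tests and the reference standard cover different anatomy. Imaging answers whether cancer remains in the breast; RCB 0 asks whether any remains in breast or nodes. When nodal disease outlasts breast disease, a correct breast reading becomes a false positive for pCR.

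Two things are at stake. Specificity and AUC against RCB 0 then depend partly on how many such patients are enrolled, which is not a property of the imaging. Also, the loss is not equal for the two modalities. The better a test recognises a clear breast, the more often it makes this call, so the CEDM-mammography contrast in section 8.3 is compressed. More patients would not remove the effect. Section 8.2 says the results will help design a multi-institutional study.

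**Working it through.** **The plan's own figures (section 8.2).** With 100 patients and 40% pCR there are 40 pCR and 60 non-pCR patients. The worst-case 95% half-width with continuity correction is 1.96·sqrt(0.25/n) + 1/(2n).

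- Sensitivity, n = 40: 0.155 + 0.0125 = 0.167 (stated 0.17).
- Specificity, n = 60: 0.1265 + 0.0083 = 0.135 (stated 0.14 at most).
- AUC at 0.5: 0.116 by Hanley-McNeil or 0.113 by a binormal formula (stated 0.12).

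These reproduce and are not in dispute.

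**Inputs for the check.**

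- 60 non-pCR patients: section 8.2.
- k, the number of those 60 with a clear breast and residual nodes: not in the documents. Assumed 3, 6 or 9 (5%, 10%, 15%).
- Se, the chance of a complete-response reading when the breast is clear, and Sp, the chance of a residual-disease reading when it is not.
- Mammography: 0.542 and 0.863 from section 1.2. Treating these as breast-level figures is an assumption.
- A more accurate test: 0.90 and 0.90, assumed.

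**Formula.** The 60-k patients with residual breast cancer are scored correctly with probability Sp. The k nodal-only patients are scored correctly only if the breast is misread, with probability 1-Se. So

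specificity against RCB 0 = [(60-k)·Sp + k·(1-Se)]/60 = Sp - (k/60)(Se+Sp-1).

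Se+Sp-1 is 0.405 for mammography and 0.80 for the assumed test.

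| k | Loss, mammography | Specificity (from 0.863) | Loss, 0.90/0.90 test | Specificity (from 0.90) | Difference (from +0.037) |
|---|---|---|---|---|---|
| 3 | 0.020 | 0.843 | 0.040 | 0.860 | +0.017 |
| 6 | 0.041 | 0.822 | 0.080 | 0.820 | about 0 |
| 9 | 0.061 | 0.802 | 0.120 | 0.780 | -0.022 |

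Under these inputs the specificity advantage vanishes when (k/60)(0.80-0.405) = 0.037, that is at k = 5.6, and reverses above that.

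**AUC.** If nodal-only patients' breast scores are distributed like those of pCR patients, AUC against RCB 0 is (1-k/60)·A + (k/60)·0.5, where A is the breast-level AUC. Each modality loses (k/60)(A-0.5). The AUC difference shrinks by k/60, that is by 5%, 10% or 15%, but does not change sign.

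**Sensitivity.** Its denominator is the 40 RCB 0 patients, whose breasts are clear by definition, so k does not enter.

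**Precision of a breast-only reference.** The groups become 40+k and 60-k. For k = 3, 6, 9 the maximum half-widths are 0.161, 0.155, 0.150 for sensitivity and 0.139, 0.143, 0.147 for specificity, with about 0.115 for AUC. Precision stays close to plan.

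**The case against.** The strongest reply is that whole-patient pCR is a legitimate target. Section 2.1 sets out to predict pCR, section 1.1 motivates it by its link to disease-free survival, and section 1.3 names pCR and RCB as the metrics. On that view, calling pCR in a patient with residual nodal cancer is a real prediction error, and specificity against RCB 0 is exactly what the plan wants. This stands. A reader might infer that RCB 0 is the wrong reference and should be replaced; the documents do not support that.

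Second, the protocol does not print the components of the RCB index; it names the method and links to a calculator. The premise rests on the definition of that named index. If it were set aside, the plan would still not say whether pCR means breast alone or breast plus nodes, and that would need stating.

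Third, section 6.1 does not confine RECIST lesions to the breast, and Table 1 concerns imaging before therapy and has no CEDM column. Both are true. But no nodal reading rule is given anywhere, and every listed CEDM measurement is of the breast.

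Fourth, the size is assumed. That is correct: no nodal-only rate is given, and at k = 3 the loss is only 0.02 to 0.04.

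Fifth, the planned Spearman correlation of imaging size with pathologic size is a breast-level check. It does not supply breast-level sensitivity, specificity or a modality contrast for pCR.

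Two further inferences would go too far. Sensitivity is not distorted. Nor is it true that neither test can score these patients correctly: a false residual reading in the breast is counted as correct by accident.

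**Conclusion.** The point holds as a gap in reporting, not as an error in the chosen target. With RCB 0 as the only reference, nodal-only residual disease lowers specificity by (k/60)(Se+Sp-1) for both modalities. For k of 3 to 9 that is about 0.02 to 0.06 at the protocol's mammography figures and 0.04 to 0.12 at an assumed 0.90/0.90. AUC falls too.

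The loss is larger for the more accurate modality. In the worked example a specificity advantage of 0.037 is gone at k = 6 and reversed at k = 9. That reversal concerns specificity alone: the sensitivity contrast is untouched and the AUC difference only shrinks.

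The conclusion rests on RCB counting nodal disease by definition, on nodes not being read on CEDM, and on an assumed k. The direction is secure given the first two; the size cannot be fixed from the documents.

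**What to change.** In sections 6.1 and 8.3, keep RCB 0 as the plan's pCR reference. Beside it, prespecify a parallel analysis of sensitivity, specificity and AUC for CEDM versus mammography against breast-only pCR, meaning no residual invasive cancer in the breast. State how residual DCIS is handled, and count LVI-only ypT0 as non-pCR, as Appendix C requires; ypT alone would misclassify those cases.

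Add ypN and baseline nodal status to the data form, since neither section 5.4 nor section 6.3 lists them, and tabulate results under both references by baseline nodal status. This should be settled before results are seen.

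The cost is protocol wording, one more 2x2 table and ROC analysis per modality, two data items taken from existing records, and two reference definitions to explain in the report.
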